6.9.8. Overall Survival (OS)

OS is defined as the number of months elapsed between the date of the first dose and the date of death (whatever the cause). Patients who are alive or lost to follow-up as of the data cutoff date will be right-censored. The censoring date will be determined from the date the patient was last known to be alive. Based on these considerations, OS will be calculated as follows:

$$\text{OS (months)} = (\text{Death or Censoring Date} - \text{First Dose Date} + 1) / 30.4375$$

If warranted by data, the duration of OS will be summarized descriptively using the Kaplan-Meier method with the 95% CI about the median calculated using Greenwood's formula.

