9.4.3 Efficacy Analyses

The efficacy analyses will be conducted on the efficacy population unless otherwise specified.

Tumor response will be assessed using RECIST 1.1 (Table 11-8). The objective response rate (ORR) is defined as the number of patients who achieve a best overall response of complete response (CR) or partial response (PR) that are confirmed divided by the total number of efficacy analysis population. ORR, accompanied by 2-sided 95% exact binomial CIs, will be summarized. The analysis of ORR will be conducted both by the responses determined by IRC and investigator.

Waterfall plots will be used to depict graphically the maximum decrease from baseline in the sum diameters of target lesions.

DOR will be calculated for patients who achieve CR or PR. For such patients, DOR is defined as the number of months from the start date of CR or PR (whichever response status is observed first) and subsequently confirmed, to the first date that PD is objectively documented. If a patient dies, irrespective of cause, without documentation of PD beforehand, then the patient's date of death will be used to denote the response end date.

PFS will be derived for each patient as the number of months from the date of the first dose of study drug to the earlier of documented PD or death due to any cause. Patients who are alive and without documented PD as of a data analysis cutoff date will be right-censored.

OS will be derived for each patient as the number of months from the date of the first dose of study drug to the date of death, irrespective of cause. Patients who are alive or lost to follow-up as of a data analysis cutoff date will be right-censored. The censoring date will be determined from the last date the patient was known to be alive or data analysis cutoff date, whichever occurs first.

The detailed censoring rule for lifetime data such as DOR, PFS and OS will be specified in SAP. DOR, PFS, and OS will be summarized descriptively using the Kaplan-Meier method with 95%

CI. Median follow-up for each endpoint will be estimated according to the Kaplan-Meier estimate of potential follow-up ([Schemper and Smith 1996](#)).

Analyses of other secondary and exploratory endpoints will be provided in the SAP.

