4.2. Secondary Objectives

- To assess the anti-tumor activity of selpercatinib by determining:
 - ORR based on RECIST 1.1, as assessed by Investigator;
 - Duration of response (DOR) as assessed by IRC and Investigator;
 - Central nervous system (CNS) ORR based on RECIST 1.1 as appropriate to tumor type, as assessed by IRC (for patients with brain metastases);
 - CNS DOR as assessed by IRC (for patients with brain metastases);
 - Time to response (TTR) based on RECIST 1.1 as appropriate to tumor type, as assessed by IRC and Investigator;
 - Time to best response (TTBR) based on RECIST 1.1 as appropriate to tumor type, as assessed by IRC and Investigator;
 - Clinical Benefit Rate (CBR), as assessed by IRC and Investigator;
 - Progression-free survival (PFS) as assessed by IRC and Investigator;
 - Overall survival (OS) following initiation of selpercatinib.
- To determine the safety profile and tolerability of selpercatinib.
- To characterize the PK properties of selpercatinib.

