6.14. Interim Analyses and Data Monitoring

An interim analysis is planned to trigger early interaction with regulatory authorities. The data cutoff date is expected to be 31 July 2020, determined such that approximately half of enrolled patients will have received at least one post-baseline tumor assessment.

The primary analysis will be performed after all enrolled patients have been followed up for a sufficient amount of time (with at least two post-baseline tumor assessments, except for patients discontinued early). The primary analysis may be updated upon request from regulatory authorities.

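### SAP 6.9.8 censors overall survival at the date last known alive without the protocol's cap at data cutoff, so OS would be biased upward if survival contacts dated after cutoff are in the dataset

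*SAP*

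**What the plan says.** Protocol 9.4.3 gives the OS censoring date in full: "The censoring date will be determined from the last date the patient was known to be alive or data analysis cutoff date, whichever occurs first". It adds: "The detailed censoring rule for lifetime data such as DOR, PFS and OS will be specified in SAP".

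SAP 6.9.8 has two sentences on the matter. The first settles who is censored: "Patients who are alive or lost to follow-up as of the data cutoff date will be right-censored". The second settles when: "The censoring date will be determined from the date the patient was last known to be alive". The cap at the cutoff is absent from the second sentence. The revision history in SAP section 3 does not mention a change to OS censoring, and no general SAP rule was found that removes records dated after a cutoff.

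OS is listed among the secondary objectives in SAP 4.2. SAP 6.9.8 plans only a description: "If warranted by data, the duration of OS will be summarized descriptively using the Kaplan-Meier method", with a confidence interval about the median.

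**The concern.** The two SAP sentences use different clocks: event status stops at the cutoff, but the censoring date need not. Consider a patient alive at cutoff and telephoned two months later. Under the SAP's words, those two months count as time at risk. Had the patient died in that interval, the death would not count, because the patient was alive at cutoff and so is censored. Time after cutoff can therefore enlarge the risk set but cannot contribute a death, and Kaplan-Meier estimates at the affected follow-up times are pushed up.

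Such contacts are plausible. Patients on treatment are seen on Day 1 of each 28-day cycle (Protocol Table 7-1), and survival follow-up after treatment runs about every 3 months, by telephone if convenient (Protocol 7.6). The SAP expects an interim cutoff ("The data cutoff date is expected to be 31 July 2020"), a later primary analysis and possible regulatory updates (SAP 6.14), so collection continues past at least one cutoff. At stake are the reported OS curve and the risk that two programmers derive different OS times from the same data.

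**Working it through.** **No plan figure to reproduce.** The documents give no expected OS, number of deaths or OS target. They also give no interval between cutoff and database lock. The size therefore rests on assumptions.

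**Step 1: the mechanism by hand.** Assume exponential survival with a 24-month median, 12 months of uniform accrual, cutoff 12 months after last entry, and status known for everyone for 3 months past cutoff.

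- Hazard: ln 2 / 24 = 0.02888 per month.
- Alive at cutoff: (e^(-12 x 0.02888) - e^(-24 x 0.02888)) / (12 x 0.02888) = (0.7071 - 0.5000) / 0.3466 = 0.598. Dead by cutoff: 0.402.
- Person-time to cutoff: 0.402 / 0.02888 = 13.92 months per patient.
- Extra person-time after cutoff: 0.598 x (1 - e^(-3 x 0.02888)) / 0.02888 = 0.598 x 2.87 = 1.72 months.
- Deaths after cutoff, not counted: 0.598 x 0.083 = 0.050 per patient.

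The median implied by deaths over person-time is then:

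- Protocol rule: 0.6931 x 13.92 / 0.402 = 24.0 months.
- SAP rule read literally: 0.6931 x (13.92 + 1.72) / 0.402 = 27.0 months.
- Extra time and extra deaths both counted: 0.6931 x 15.64 / 0.452 = 24.0 months.

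The error comes from counting the time without the deaths. A simulation of this case with monthly contacts gave 26.3 months, lower than 27.0 because contacts lag.

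**Step 2: 12-month Kaplan-Meier OS at the planned size.** From the documents: about 75 patients (Protocol 3.6). Assumed: 12-month uniform accrual, cutoff 4 months after last entry, exponential OS, and every survivor followed through a gap of 1 or 3 months after cutoff. There were 1,500 simulated trials per scenario. The true value is 2^(-12/median).

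| Median OS (assumed) | True | Protocol rule | SAP rule, 1-month gap | SAP rule, 3-month gap | Rise over protocol rule (points) |
|---|---|---|---|---|---|
| 20 months | 66.0% | 65.9% | 68.1% | 70.7% | +2.2 to +4.8 |
| 30 months | 75.8% | 75.9% | 77.5% | 79.5% | +1.6 to +3.6 |
| 40 months | 81.2% | 81.1% | 82.4% | 84.0% | +1.3 to +2.9 |

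The standard error is 5.4 to 6.6 points, so the rise is about 0.2 to 0.7 of one standard error. A rerun agreed to within 0.2 points.

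**Step 3: less complete contact.** With contacts every 3 months, the SAP rule exceeds the protocol rule by about 0.3 to 0.5 points (1-month gap) or 1.9 to 2.9 points (3-month gap). If one third of patients have contact after cutoff, the rise is about 0.5 to 1.9 points. With no records after cutoff, it is zero.

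**Step 4: a later time point.** Assume medians of 18, 24 or 36 months, cutoff 6 or 12 months after last entry, and monthly contacts. In 200,000 simulated patients per scenario, 18-month OS without the cap is too high by 0.5 to 3.3 points with 1 month of contacts after cutoff, and by 1.5 to 8.5 points with 3 months. With 6 months, the excess is 2.0 to 11.8 points. Eighteen months is the longest possible follow-up when cutoff falls 6 months after last entry (12 + 6), so few patients remain at risk. With the cap, the estimates are 0.50, 0.59 to 0.60 and 0.70 to 0.71, against true values of 0.500, 0.595 and 0.707.

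**The case against.** The strongest reply is that the SAP sentence is shorthand. The sentence before it is framed by the data cutoff, and the next can be read inside that frame, as last known alive at cutoff. SAP 6.9.5 and 6.9.7 likewise date censoring by the last evaluable assessment without repeating a cap, and the SAP uses the cutoff as its reference elsewhere. The protocol's rule has not been withdrawn. A reader might infer that the SAP deliberately departs from the protocol; nothing in the documents shows that.

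This reply reduces the point but does not remove it. The protocol thought the cap needed its own words and left the detailed censoring rules to the SAP, where the cap is missing. Nor can a cap be presumed throughout: time on treatment for ongoing patients ends at the last visit date with no stated limit (SAP 6.11.1.1).

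Three further objections stand:

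- The upper figures require contact with every survivor through the whole gap.
- The 12- and 18-month rates are illustrations, because SAP 6.9.8 names no landmark rate. In the Step 2 scenario, the median it does name is reached under the protocol rule in only about 17-18%, 3.5% and 1-2% of trials, for true medians of 20, 30 and 40 months.
- OS here is single-arm and descriptive, with no test or decision attached.

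**Conclusion.** The omission is real, and read literally the SAP's OS rule conflicts with the protocol's. The consequence is conditional: OS would be biased upward if survival contacts dated after cutoff are kept in the analysis dataset. A reader might go further and conclude that reported OS is biased upward, or that it is inflated by some 5 points. The documents do not support either, since they do not say that such contacts will be used and give no cutoff-to-lock gap.

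For 12-month OS, under the assumed accrual, medians and a gap of up to 3 months, the range is zero to about 5 points. Later time points or longer gaps could show more, as Step 4 illustrates. The independently reviewed response rate does not use this rule and is unaffected. Severity: minor.

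**What to change.** In SAP 6.9.8, set the OS censoring date to "the last date the patient was known to be alive or data analysis cutoff date, whichever occurs first", and add that patients who die after cutoff are censored under the same rule. Alternatively, state once in the SAP that all records dated after cutoff are excluded.

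Either change removes the upward bias. The first is preferable where later contacts are held, because a contact after cutoff shows that the patient was alive at cutoff. Excluding those records leaves estimates slightly low: deaths are counted to the cutoff while last contacts lag behind it. In the simulation with a true median of 18 months, the implied median was about 17.4 to 17.6 months when no records after cutoff were available.

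The cost is one sentence in the SAP and one line of derivation code, with no new data or site burden.

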6.9.9. CNS ORR and CNS DOR

Analyses of CNS ORR and CNS DOR will be conducted on the CNS response analysis population. The CNS ORR and CNS DOR will be assessed by IRC and will be analyzed using the same method described above for the analyses of ORR and DOR if data warrant.

Waterfall plot for change of CNS tumor burden from baseline will be provided.

6.10. Patient-Reported Outcomes

6.10.1. EORTC QLQ-C30

Data from the EORTC QLQ-C30 (Aaronson et al. 1993) instrument will be scored as described by the European Organization for Research and Treatment of Cancer (EORTC) scoring manual (Fayers et al. 2001).

Following the scoring instructions given by the EORTC Quality of Life Study Group, the raw EORTC QLQ-C30 subscale scores will be linearly transformed to 0–100. Missing values will be handled as outlined in the EORTC QLQ-C30 scoring manual if at least 50% of the items on a scale or subscale are reported; no values will be imputed. The raw score will be computed if at least 50% of the items on a scale or subscale are complete. The scoring for EORTC QLQ-C30 is detailed in Appendix 1.

Descriptive analyses will report median/quartile, mean/standard deviation (SD), and will include mean change/standard error (SE) from baseline for each subscale at each study visit for the predefined study cohorts. Additionally, mean scores across time will be presented in a line plot for each subscale.

For each subscale, mean change from baseline scores across time will be presented in a line plot.

For all change-from-baseline measures, the analysis set will include all treated patients who have baseline and at least one post-baseline PRO assessment on the QLQ-C30 subscale being evaluated.

A clinically meaningful difference will be defined as 10-point difference from the baseline assessment value for each patient. Each scale at every assessment time point will be compared to its baseline value and be categorized as follows (Osoba et al. 1998):

- **Worsening:** Defined as an increase of ≥ 10 points for the symptom scales or a decrease of ≥ 10 points for the functional scales and global health status/QoL scale.
- **Improvement:** Defined as a decrease of ≥ 10 points for the symptom scales or an increase of ≥ 10 points for the functional scales and global health status/QoL scale.
- **Stable:** Defined as no change or an increase/decrease of < 10 points.

The number and percentage of patients improving, stable and worsening relative to their own baseline measurement will be reported at each post-baseline clinic visit time point for all patients reporting data. For each subscale, the number and proportion of patients experiencing definite improvement and time to definite improvement (defined as the first improvement from baseline of ≥ 10 points without any further deterioration in score ≥ 10 points) will be summarized.

Similarly, number and proportion of patients experiencing definite worsening (defined as the first worsening from baseline, a ≥ 10 point decrease, without any further improvement of ≥ 10 points) and time to definite worsening will also be summarized.

Time to first improvement and to first worsening, respectively, will be evaluated using Kaplan-Meier method. For time to first improvement, patients who did not improve will be censored at

the date of their last EORTC assessment; Similarly, for time to first worsening, patients who did not worsen will be censored at the date of their last EORTC assessment.

Questionnaire compliance will be summarized. Compliance rates will be calculated at each assessment time point. Compliance at an assessment time point is defined as the number of patients who were assessed divided by the expected number of patients at that time point. The expected number of patients:

- at baseline is equal to the number of patients enrolled
- at any post-baseline visit is equal to the number of patients who are alive and have not progressed

A patient who answers at least one item at a time point is considered to have been assessed. Reasons for non-compliance will be tabulated by assessment time point.

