The number and proportion of patients experiencing worsening or improvement from baseline will be reported at each study visit at which the bowel diary is collected. Kaplan-Meier method will be used to evaluate time to first improvement (among the baseline diarrhea population) and time to first worsening (for the entire Cohort 2), respectively. For patients in the baseline diarrhea population, those who didn't experience any improvement or worsening will be censored at the date of their last bowel diary assessment. For patients in Cohort 2 who didn't have diarrhea at baseline, time to first worsening will be censored at the date of data cutoff.

For patients with improvement, the duration of improvement (defined as time from first improvement to the return to or below the baseline categorical level) will be reported as median, range, mean/SD days. Similarly, the duration of worsening (defined as time from first worsening to the return to or above the baseline categorical level) will be reported as median, range, mean/SD days.

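### QLQ-C30 improvement analyses include patients whose baseline score leaves no room for a 10-point gain, so improvement rates and times mix symptom relief with how many patients entered symptom-free (exploratory outputs, low priority)

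*SAP*

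**What the plan says.** SAP 6.10.1 puts each subscale on a bounded range: "the raw EORTC QLQ-C30 subscale scores will be linearly transformed to 0–100". Improvement is judged against the patient's own baseline: "Defined as a decrease of ≥ 10 points for the symptom scales or an increase of ≥ 10 points for the functional scales"; the global scale follows the functional rule. Worsening is the reverse, and anything smaller is stable.

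Four statements fix who is counted:

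- Measures of change: "the analysis set will include all treated patients who have baseline and at least one post-baseline PRO assessment on the QLQ-C30 subscale being evaluated".
- The three-category table: "The number and percentage of patients improving, stable and worsening relative to their own baseline measurement will be reported". Its denominator is everyone with data at the visit, since the percentages "will be reported at each post-baseline clinic visit time point for all patients reporting data".
- Per subscale, a summary of "the number and proportion of patients experiencing definite improvement and time to definite improvement", with a matching summary for definite worsening.
- Kaplan-Meier time to first improvement and to first worsening. The rule for non-improvers begins "For time to first improvement, patients who did not improve will be censored at" and names the last EORTC assessment; worsening is handled the same way.

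None of these sets a condition on the baseline score. Appendix 1 of the SAP, and the protocol text on patient-reported outcomes (Sections 7.7.4, 8.7, 9.1.3 and Appendix J), set none either.

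For the bowel diary, SAP 6.10.2 reads differently: "Kaplan-Meier method will be used to evaluate time to first improvement (among the baseline diarrhea population"), while time to first worsening covers all of Cohort 2.

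**The concern.** On a bounded scale with a fixed 10-point threshold, a patient who starts within 10 points of the best score cannot have the improvement event. On a single-item symptom, that is anyone without the symptom at entry. Such patients still count in the denominator of the improvement proportion and in the risk set for time to first improvement.

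The improvement figures then answer two questions at once: how many patients had something to improve, and how many of those improved. The protocol's exploratory objective is to look at disease-related symptoms and quality of life, which is mainly the second question. The share without room can differ between subscales and cohorts, so a lower rate on one subscale may reflect baseline status and not less relief. The same holds in mirror image for worsening.

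**Working it through.** The documents state no improvement rate, median or QLQ-C30 sample size, so there is no plan figure to reproduce. The check has three steps.

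**1. Baseline scores with no room to change.** Inputs are the item counts and transforms in SAP Appendix 1. The divisor is the item range: 6 for global health, 3 for the other scales. With m items, the step between attainable complete-data scores is 100 / (m × range). Improvement is impossible if the distance to the best score is below 10, and worsening if the distance to the worst score is below 10.

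| Scale | Step | No improvement from | No worsening from |
|---|---|---|---|
| Global health (2 items) | 100/12 = 8.33 | 91.7, 100 | 0, 8.3 |
| Physical functioning (5) | 100/15 = 6.67 | 93.3, 100 | 0, 6.7 |
| Emotional functioning (4) | 100/12 = 8.33 | 91.7, 100 | 0, 8.3 |
| Role, cognitive, social functioning (2 each) | 100/6 = 16.67 | 100 | 0 |
| Fatigue (3) | 100/9 = 11.11 | 0 | 100 |
| Nausea/vomiting, pain (2 each) | 100/6 = 16.67 | 0 | 100 |
| Six single items | 100/3 = 33.33 | 0 | 100 |

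All 15 scales have at least one baseline score from which improvement cannot occur. For example, physical functioning from 93.3 to 100 is +6.7, and emotional functioning from 91.7 to 100 is +8.3; both fall short of 10.

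**2. Effect on the proportion.** Let f be the share of analysed patients without room and r the improvement rate among those with room. Then

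reported rate = (1 − f) × r.

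The documents give neither f nor r. Assumed values:

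| r | f = 20% | f = 40% | f = 60% |
|---|---|---|---|
| 30% | 24% | 18% | 12% |
| 50% | 40% | 30% | 20% |
| 70% | 56% | 42% | 28% |

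**3. Effect on time to first improvement.** If censoring is unrelated to baseline room, the Kaplan-Meier curve estimates F(t) = (1 − f) × F_room(t). The median solves F_room(t) = 0.5 / (1 − f), which has no solution once f reaches 50%. For an assumed exponential time with median 2.0 months among patients with room, t = −2.0 × log2(1 − 0.5 / (1 − f)):

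- f = 10%: 2.3 months
- f = 20%: 0.5/0.8 = 0.625, so t = −2.0 × log2(0.375) = 2.8 months
- f = 30%: 3.6 months
- f = 40%: 0.5/0.6 = 0.833, so t = −2.0 × log2(0.167) = 5.2 months
- f ≥ 50%: not reached

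Restricting the risk set to patients with room returns 2.0 months in each case.

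**The case against.** The strongest reply is that nothing here is an error. The outcome is exploratory, the study has one arm, and no test or decision uses these rates. The SAP states its denominator, and the share of all reporting patients who improved, held or worsened is a legitimate description of the group. Calling it diluted presupposes a different target, improvement among patients who could improve. This stands for the three-category table, which should be kept. It is weaker for definite improvement and time to first improvement, where part of the risk set can never have the event.

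Other planned output also helps. Means, quartiles and mean changes per subscale and visit would reveal a heavy floor or ceiling at baseline, though not the exact number with room.

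A reader might infer that the SAP contradicts itself, because diary improvement is limited to patients with diarrhea at baseline. The documents do not support that firmly. The restriction partly follows data collection: the protocol synopsis and the notes to Table 7-1 collect the diary only from MTC patients with baseline diarrhea, and SAP 6.1.1 bases all diary analyses on that group. Nor does the diary section exclude patients already at the worst category from time to first worsening. It is a useful contrast, not a rule that the QLQ-C30 section breaks.

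A reader might also infer that patients without room are all counted as stable. They are not: a patient at symptom score 0 can worsen and would be classed so.

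Finally, restricting has its own bias. Without a control arm, patients selected for a poorer baseline will tend to look better later by regression to the mean. That stands and must accompany the restricted rates.

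**Conclusion.** The point holds as a low-priority improvement. The existence and direction of the effect follow from the SAP's own threshold, scoring and analysis sets: improvement proportions are lowered by the factor (1 − f), and time to first improvement is lengthened or its median made unreachable. The size is not known. The figures of 40%, 30% and 20% rest on an assumed 50% rate and assumed f of 20%, 40% and 60%; the medians rest in addition on an exponential time to improvement and on censoring unrelated to baseline room.

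The documents do not support going further and calling the improving, stable and worsening table wrong, or treating any low improvement rate as uninterpretable. The analysed patients already need a baseline and a post-baseline value on the subscale. The outputs are descriptive and exploratory, and the primary ORR conclusion does not depend on them.

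**What to change.** In SAP 6.10.1:

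- Keep the three-category table for all patients reporting data, labelled as a description of that whole group. Replacing it with filtered categories would lose its common denominator.
- For each subscale, add the number with room to improve and the improvement rate among them.
- Base definite improvement and time to first improvement on patients with a baseline symptom score of at least 10, or a functional or global score of at most 90.
- Base definite worsening and time to first worsening on patients with a baseline symptom score of at most 90, or a functional or global score of at least 10.

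These cut-offs separate possible from impossible exactly, because they are the distance to the end of the scale. Fatigue 11.1 can reach 0, physical functioning 86.7 can reach 100, and emotional functioning or global health 83.3 can reach 100.

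The cost is a few sentences and a filter, with no new data. The price in interpretation is a smaller n that differs by subscale: in a cohort of 20 with an assumed f of 60%, 20 × 0.4 = 8 patients remain. The report should also note regression to the mean among patients selected for a poorer baseline.
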